7. A single 12-lead ECG will be performed in the supine position after 10 minutes of rest.
8. Participants must fast for a minimum of 8 hours prior to samples being collected.
9. Samples should be collected prior to study drug administration.
10. Urinalysis will be performed locally by dipstick analyses from a sample of mid-stream urine. In case of abnormal results, microscopy and other assessments will be performed at the local laboratory and the abnormality recorded as an AE.
11. A PK sample will be collected prior to study drug administration for trough measurement of obicetrapib in plasma. At Visits 2, 5, and 7, participants should take study drug after a trough PK sample has been drawn.
12. The PK sample at Visit 4 is not designated in the protocol, however the PK will be assessed using residual serum from the Day 84 limited chemistry panel to confirm patients are taking IP.

AE = adverse event; ApoA1 = apolipoprotein A1; BMI = body mass index; CV = cardiovascular; ECG = electrocardiogram; EOS = End of Study; EOT = End of Treatment; ET = Early Termination; FSH = follicle-stimulating hormone; hsCRP = high sensitivity C-reactive protein; Lp(a) = lipoprotein (a); PK = pharmacokinetic(s); TSH = thyroid-stimulating hormone; UACR = urine albumin-creatinine ratio; UPCR = urine protein-creatinine ratio; V = Visit.

2.2.2 *Sample Size Determination*

Enrollment of approximately 300 participants globally is planned for this study.

Assuming an approximate 5% drop out rate, approximately 285 participants will be evaluable for efficacy. This sample size of at least 285 evaluable participants will provide more than 90% power to detect a 30% reduction of LDL-C (standard deviation 15%) levels in the obicetrapib group compared to the placebo group at a 1-sided significance level of 0.025. This sample size will also contribute to sufficient participant exposure and safety data.

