3.2 Analysis Populations

3.2.1 *Intent-to-Treat (ITT) Population*

The ITT Population will include all participants who are randomized into the study. Treatment classification will be based on the randomized treatment.

3.2.2 *The Full Analysis Set (FAS)*

The FAS will include all participants who are randomized into the study, take any study drug, and have at least 1 post-treatment lipid data assessment. Treatment classification will be based on the randomized treatment.

3.2.3 *Modified Intent-to-Treat (mITT) Population*

The mITT Population will include all randomized participants who receive at least 1 dose of any study drug and have data for both the Day 1 and Day 84 LDL-C assessments. Treatment classification will be based on the randomized treatment.

3.2.4 *Modified Intent-to-Treat (mITT) On-Treatment Population*

The mITT On-Treatment Population will include all randomized participants who have data for both the Day 1 and Day 84 LDL-C assessments. Participants in the obicetrapib group with PK values less than 3 standard deviations from the mean obicetrapib concentration should be excluded. Treatment classification will be based on the randomized treatment.

Rationale: in previous studies, such as ROSE (protocol number TA-8995-201), TULIP (protocol number TA-8995-03), and ROSE2 (protocol number TA-8995-202), it was demonstrated that the minimally observed obicetrapib concentration for C_{max} was less than three standard deviations from the mean at respectively Week 4 and Week 12 [3-5].

3.2.5 *Per-Protocol (PP) Population*

The PP Population will include all participants in the mITT Population who did not experience a major protocol deviation that potentially impacted the primary efficacy endpoint. The PP Population, along with the reason for exclusion, will be finalized prior to study unblinding.

3.2.6 *Safety Population*

The Safety Population will include all participants who receive at least 1 dose of any study drug. Treatment classification will be based on the actual treatment received. The Safety Population will be the primary population used for the safety analyses.

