3.3.7 Study Drug Exposure and Compliance

Participants' exposure to randomized study drug will be summarized with descriptive statistics for the Safety Population and mITT On-Treatment Population. Days of exposure to study drug will be calculated as

$$\text{date of last dose of study drug} - \text{date of first dose of study drug} + 1.$$

For participants' whose date of first dose from the initial bottle dispensed was not available, the date of randomization will be used to assign the date of first dose. For participants who failed to provide the date of last dose of study drug, the earliest date between the end of treatment date and the date of the end of study/early termination will be used.

Days of exposure to study drug will be summarized by treatment group based on the Safety Population with counts and percentages of participants with exposure in the following categories:

- <3 weeks
- 3 – <5 weeks
- 5 – <7 weeks
- 7 – <9 weeks
- 9 – <11 weeks
- 11 – <13 weeks
- 13 – <19 weeks
- 19 – <25 weeks
- 25 – <28 weeks
- 28 – <34 weeks
- 34 – <40 weeks
- 40 – <50 weeks
- 50 – <54 weeks
- >=54 weeks

The percentage overall compliance to study drug will be calculated using the following formula:

$$\frac{\# \text{ tablets dispensed} - \# \text{ tablets returned}}{\# \text{ expected dosing days}} \times 100$$

If study drug is not returned, the number of tablets returned and lost will be considered 0 for the compliance calculation. The expected dosing days will be calculated as the earliest date between the end of treatment date and the date of early termination – the date of randomization- missed doses+1 (*missed doses defined as number of doses missed during IP interruptions due to AE or IP interruptions that are longer than 14 days*).

Percent compliance to the study drug regimen will be summarized by treatment group and in total based on the Safety Population and mITT On-Treatment with descriptive statistics and with counts and percentages of participants with compliance in the following categories:

- <80%
- 80% to 120%
- >120%

Study drug interruptions due to AE or IP interruptions longer than 14 days will be listed.

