- **Analysis set and handling of intercurrent events:** A hypothetical strategy will be used. All available values of LDL-C at Baseline and Day 84 will be included in the calculation of the percentage change from Baseline to Day 84.
- **Population level summary:** The difference in LS mean percentage change in LDL-C from Baseline to Day 84 between treatment groups.

This hypothetical estimand represents the treatment effect of obicetrapib relative to placebo at Day 84 in the randomized participants had they remained on their randomized treatment for the entire planned treatment period. This estimand uses a hypothetical strategy to handle intercurrent events and is intended to provide an estimation of the achievable study treatment effect if participants take the treatment as planned. The resulting missing values (corresponding to unobserved values or excluded values following study drug discontinuation or the use of prohibited medication) will be implicitly handled by using a MMRM approach under the assumption of missing at random. The model will be similar to the MMRM approach described previously for the supplemental analysis of the primary efficacy endpoint. The supplementary analysis for the primary efficacy endpoint assessed by secondary estimand will be performed using the mITT On-Treatment populations.

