5.2 Pre-Final Analysis

After the database is locked and exclusions from analysis populations have been finalized, the randomized treatment assignments will be unblinded and the pre-final analysis will be generated. Pre-final tables, figures, and listings (TFLs) will be provided approximately 3 weeks after database lock.

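### The mITT On-Treatment Population selects on drug intake in the obicetrapib arm only, so its supportive ANCOVA is not like-for-like, and the SAP gives no route for applying the rule before unblinding

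*SAP*

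**What the plan says.** The base of the population in SAP 3.2.4 is broad: "The mITT On-Treatment Population will include all randomized participants who have data for both the Day 1 and Day 84 LDL-C assessments". The mITT requirement of at least one dose (SAP 3.2.3) is not carried over. The only intake condition is the drug-level rule: "Participants in the obicetrapib group with PK values less than 3 standard deviations from the mean obicetrapib concentration should be excluded". Nothing in 3.2.4 refers to permanent stop, interruption or tablet count in either arm.

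The Day 84 drug level comes from a footnote to the SAP's Table 1, under which "the PK will be assessed using residual serum from the Day 84 limited chemistry panel to confirm patients are taking IP". The three-standard-deviation limit is justified by peak concentrations in earlier studies, where "the minimally observed obicetrapib concentration for C_{max} was less than three standard deviations from the mean".

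The population is used in three places:

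- a supplementary ANCOVA of the primary endpoint, without imputation (SAP 3.4.1);
- the secondary estimand: "The supplementary analysis for the primary efficacy endpoint assessed by secondary estimand will be performed using the mITT On-Treatment populations";
- exposure and compliance tables: "Percent compliance to the study drug regimen will be summarized by treatment group and in total based on the Safety Population and mITT On-Treatment" (SAP 3.3.7).

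On timing, SAP 5.2 says: "After the database is locked and exclusions from analysis populations have been finalized, the randomized treatment assignments will be unblinded". For the Per-Protocol set, SAP 3.2.5 adds its own safeguard: "The PP Population, along with the reason for exclusion, will be finalized prior to study unblinding". Section 3.2.4 has no such sentence. The protocol (9.1) does not contain this population, and SAP Section 6 does not list it among the four changes from the protocol.

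**The concern.** A population named for being on treatment should ask the same question of both arms. Here an obicetrapib participant with too little drug at Day 84 is meant to leave, while a placebo participant who took no tablets, or stopped in the first week, stays if the two LDL-C values exist. Such participants are to be expected. Protocol 4.3 keeps those who stop study drug on the visit schedule, and SAP 3.1.8 commits to measuring endpoints in them.

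Randomization then no longer protects the comparison. Any difference in LDL-C course between people who take tablets and people who do not is removed from one mean and left in the other. The compliance and exposure tables for this set have the same defect: one arm is filtered on intake and then shown beside an unfiltered arm.

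The second issue is procedural. Whether the rule applies to a given person depends on the arm, so population membership requires the treatment code at a stage when the SAP says everyone who evaluates data is still blinded.

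**Working it through.** **Inputs from the documents.** 300 randomized 2:1, 5% dropout, 285 evaluable (190 and 95), difference 30 points, SD 15, one-sided 0.025 (SAP 2.2.2). **Assumptions, because the documents give no figures:** share of non-takers p, equal in both arms; non-takers get no drug effect; their LDL-C changes by g points for other reasons; the concentration CV among takers.

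**1. The plan's own figure.** 300 × 0.95 = 285. Standard error = 15 × √(1/95 + 1/190) = 1.88. The assumed difference is 30/1.88, or about 16 standard errors, so power is about 100% and the stated lower bound of 90% is met. The plan gives no figure for the On-Treatment set.

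**2. Effect of filtering one arm.** Takers change by −30 on obicetrapib and 0 on placebo. Suppose the rule removes every obicetrapib non-taker.

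- mITT difference: [(1−p)(−30) + pg] − pg = −30(1−p)
- On-Treatment as written: −30 − pg
- Same exclusion in both arms: −30
- Gap from the two-arm exclusion: −pg. Gap from mITT: −p(30 + g)

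| p | g | mITT | As written | Both arms alike | Gap from mITT | Gap from both arms alike |
|---|---|---|---|---|---|---|
| 5% | −20 | −28.5 | −29.0 | −30.0 | −0.5 | +1.0 |
| 5% | 0 | −28.5 | −30.0 | −30.0 | −1.5 | 0 |
| 5% | +20 | −28.5 | −31.0 | −30.0 | −2.5 | −1.0 |
| 10% | −20 | −27.0 | −28.0 | −30.0 | −1.0 | +2.0 |
| 10% | 0 | −27.0 | −30.0 | −30.0 | −3.0 | 0 |
| 10% | +20 | −27.0 | −32.0 | −30.0 | −5.0 | −2.0 |

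Against mITT the effect is larger in every row. Against the two-arm exclusion the sign follows g.

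**3. Behaviour of the test with no drug effect.** Simulation with 20,000 runs, 190 and 95 participants, SD 15 and a two-sided 5% Welch test (not the full ANCOVA). Rejection rates:

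- p = 5%, g = 0: 4.7%
- p = 5%, g = +20: 7.8% (7.2% favouring obicetrapib)
- p = 10%, g = +20: 16.4% (16.2% favouring obicetrapib)
- p = 10%, g = −20: 16.4% (0.2% favouring obicetrapib)

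**4. Does the rule remove anyone?** Read it as concentration below mean − 3 SD, with mean and SD computed in this trial and non-takers at zero included. Scale the taker mean to 1. The arm mean is then 1−p and the variance is (1−p)(CV² + p). The cutoff is positive only if (1−p)² > 9(1−p)(CV² + p), that is, p < (1 − 9 CV²)/10.

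- CV 20%: p < 6.4%, at most 12 of 190
- CV 30%: p < 1.9%, at most 3 of 190
- CV one third or more: nobody at zero is removed

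Taken literally, values lying within 3 SD of the mean would be excluded, about 99.7% of a normal distribution. The SAP does not say which visit's value is used, or whether the mean and SD come from this trial or earlier ones.

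**5. Blinding.** An obicetrapib non-taker and a placebo participant both show no drug, so the rule cannot separate them without the code. Conversely, a measurable level reveals the arm. SAP 2.2.1 keeps those who evaluate data blinded until lock, SAP 5.2 fixes exclusions before the code is opened, and neither names anyone else to apply the rule.

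**The case against.** The best defence has four parts.

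First, the set is only supportive. ITT is primary, the Per-Protocol set can remove participants from either arm and is fixed blind, and exposure and compliance are also shown for the unselected Safety Population. This stands and limits the importance of the point.

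Second, a reader might infer that the secondary-estimand analysis is distorted just as the ANCOVA is. The documents do not support that. SAP 3.4.1 says values after study drug discontinuation or prohibited medication are excluded and handled by the MMRM, without limiting this to one arm, so a recorded placebo stopper loses the later values there too. The same subsection also says all available values are included, and those two statements need reconciling. On the exclusion reading, what remains in the MMRM is undocumented non-takers, filtered in one arm only.

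Third, a reader might infer that membership cannot be fixed before unblinding at all. That is too strong. A preset numeric cutoff applied by an independent unblinded party before the code is opened would satisfy SAP 5.2. The defect is that the SAP provides for neither.

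Fourth, drug levels detect non-takers better than tablet counts, and SAP 3.3.7 treats unreturned tablets as taken. This stands, and it counts against simply replacing the drug-level rule with a tablet-count rule.

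**Conclusion.** The point holds for the supportive On-Treatment ANCOVA and for the exposure and compliance tables in that population, provided the drug-level rule removes anyone. It applies less to the secondary-estimand MMRM and not at all to the primary ITT analysis or its power.

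A reader might infer that the comparison is tilted towards obicetrapib. That is predictable only relative to mITT, and only if those removed respond less than those kept. Relative to a symmetric on-treatment set, the bias favours obicetrapib if non-takers' LDL-C rises (for instance through missed background therapy), goes against it if their LDL-C falls, and is nil without drift. The documents give no information on that drift.

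The size is modest under moderate assumptions: 5% non-takers with a 20-point drift either way shifts the estimate by 1 point, about half a standard error, and 10% shifts it by 2 points. These figures assume equal shares in both arms and complete removal of obicetrapib non-takers. The change is worth making before unblinding, but the primary conclusion does not depend on it.

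**What to change.** Redefine the population in SAP 3.2.4 by conditions that apply identically in both arms, and fix membership before unblinding alongside the Per-Protocol set:

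- at least one dose of study drug taken;
- Day 84 LDL-C sample taken before any permanent stop of study drug;
- no recorded interruption covering that sample.

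A tablet-count threshold for Days 1 to 84 may be added, but only if unreturned bottles are not counted as taken. It needs a new derivation, because SAP 3.3.7 defines overall compliance only.

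Report Day 84 drug levels descriptively within the obicetrapib arm. If a drug-level-filtered set is kept as well, state the visit, the direction of the rule and a preset numeric cutoff, have an independent unblinded party apply it before unblinding, and label the result as a non-randomized comparison selected in one arm. Add the population to SAP Section 6.

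The cost is SAP wording and some programming; dosing, stop and interruption data are already collected. The downside is that a two-arm rule based on records misses undocumented non-takers whom drug levels would find.

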3.3 Participant Data and Study Conduct

3.3.1 *Participant Disposition*

Counts and percentages of participants who were randomized, completed the treatment period, discontinued treatment (including primary reason for discontinuation), completed the study, and prematurely discontinued from the study (including primary reason for discontinuation) will be summarized by treatment group and overall.

For each scheduled visit, counts and percentages of participants who did not complete the visit, partially completed the visit in-person, or completed the visit via virtual method will be summarized by treatment group and overall. The denominator for calculating percentages will be based on the number of randomized participants.

3.3.2 *Protocol Deviations*

Protocol deviations will be identified based on clinical data as defined in the Protocol Deviation Plan, where all protocol deviations will be defined as either CSR reportable or non-CSR reportable. The CSR reportable protocol deviations will be categorized and separated by treatment group. The CSR reportable deviations will include all randomized participants using counts and percentages.

3.3.3 *Analysis Populations*

Counts and percentages of participants in each analysis population will be summarized by treatment group and in total based on all randomized participants. Reasons for exclusion from PP Population will also be summarized.

3.3.4 Demographic and Baseline Characteristics

The following demographic and Baseline characteristics will be summarized with descriptive statistics or counts and percentages of participants as appropriate by treatment group and overall, for the ITT Population:

- Age and age categories (<65 years, 65 to 74 years, and 75+ years)
- Sex
- Race
- Ethnicity
- Height
- Weight
- Body Mass Index (BMI)
- Region (North America and EMEA (Europe, Middle East, and Africa))
- Diabetes (yes, no)
- HDL-C (<40mg/dL, 40 - <60 mg/dL, ≥60mg/dL)
- ApoB (<60mg/dL, 60 - <90 mg/dL, ≥90mg/dL)
- ApoA1 (<110 mg/dL, ≥110 and <125 mg/dL, ≥125mg/dL)
- Lipoprotein(a) (<75nmol/L, ≥75 and <125 nmol/L, ≥125nmol/L)
- Non-HDL-C (<100 mg/dL, ≥100 and <130 mg/dL, ≥130mg/dL)
- LDL-C (<70mg/dL, ≥70 and <100 mg/dL, ≥100mg/dL)
- TG (<150 mg/dL, ≥150mg/dL)
- HbA1c (<5.7%, ≥5.75 to ≤6.4%, >6.4%)
- Urinary albumin:creatinine ratio (normal, micro-albuminuria, macro-albuminuria)
- eGFR (<60ml/min/1.73 m², ≥60 to <90ml/min/1.73 m², ≥90ml/min/1.73 m²)
- Statin treatment (high dose (HIS), low or moderate dose (non-HIS), none (SI)). High dose statin includes atorvastatin 40 or 80 mg, rosuvastatin 20 or 40 mg. Participants will be defined as having high dose statin treatment based on the data collected in the eCRF and if any following were used at Baseline: average daily dose of atorvastatin ≥40 mg or average daily dose of rosuvastatin of ≥20 mg. Additionally, these medications can be a part of combination medications (e.g. Rosuzet 10/20mg; combination of ezetimibe 10mg and Rosuvastatin 20mg). Participants having other doses of statin or other statin treatment will be defined as low or moderate (non-HIS). Participants that are not taking statin are defined as statin intolerant (SI).
- Ezetimibe use (yes, no)
- A high-sensitivity C-reactive protein [hs-CRP] (<2mg/dL, ≥2mg/dL)
- HeFH (Genotyping confirmed or DLCN>8 points of Simon Broome definite; Simon Broome possible Familial Hypercholesterolemia (FH) diagnosis)

If they differ from the ITT Population, summaries will also be provided for the FAS, the mITT Population, the mITT On-Treatment, the PP Population, and the Safety Population. Demographic characteristics data will be provided in participant listings.

3.3.5 Medical History

Medical history will be coded to system organ class and preferred term using the current Medical Dictionary for Regulatory Activities (MedDRA) version. Counts and percentages of participants

with medical history by system organ class (SOC) and preferred term (PT) will be summarized by treatment group and in total based on all randomized participants.

A listing of all medical history data will be provided.

3.3.6 Concomitant Medications

The Prior & Concomitant Medications case report form where medication start and stop dates are recorded, will be used to determine whether the medications are prior or concomitant to the study treatment. Concomitant medications are defined as those used on or after the first dose of the study drug. Prior medications are defined as those used prior to and stopped before the first dose of study drug. All prior and concomitant medications will be coded using the current World Health Organization (WHO) Drug Dictionary. Counts and percentages of participants taking prior and concomitant medications will be summarized by anatomical therapeutic chemical (ATC) class and preferred term by treatment group and overall, for the Safety Population.

Concomitant medications will be listed.

3.3.7 Study Drug Exposure and Compliance

Participants' exposure to randomized study drug will be summarized with descriptive statistics for the Safety Population and mITT On-Treatment Population. Days of exposure to study drug will be calculated as

$$\text{date of last dose of study drug} - \text{date of first dose of study drug} + 1.$$

For participants' whose date of first dose from the initial bottle dispensed was not available, the date of randomization will be used to assign the date of first dose. For participants who failed to provide the date of last dose of study drug, the earliest date between the end of treatment date and the date of the end of study/early termination will be used.

Days of exposure to study drug will be summarized by treatment group based on the Safety Population with counts and percentages of participants with exposure in the following categories:

- <3 weeks
- 3 – <5 weeks
- 5 – <7 weeks
- 7 – <9 weeks
- 9 – <11 weeks
- 11 – <13 weeks
- 13 – <19 weeks
- 19 – <25 weeks
- 25 – <28 weeks
- 28 – <34 weeks
- 34 – <40 weeks
- 40 – <50 weeks
- 50 – <54 weeks
- >=54 weeks

The percentage overall compliance to study drug will be calculated using the following formula:

$$\frac{\# \text{ tablets dispensed} - \# \text{ tablets returned}}{\# \text{ expected dosing days}} \times 100$$

If study drug is not returned, the number of tablets returned and lost will be considered 0 for the compliance calculation. The expected dosing days will be calculated as the earliest date between the end of treatment date and the date of early termination – the date of randomization- missed doses+1 (*missed doses defined as number of doses missed during IP interruptions due to AE or IP interruptions that are longer than 14 days*).

Percent compliance to the study drug regimen will be summarized by treatment group and in total based on the Safety Population and mITT On-Treatment with descriptive statistics and with counts and percentages of participants with compliance in the following categories:

- <80%
- 80% to 120%
- >120%

Study drug interruptions due to AE or IP interruptions longer than 14 days will be listed.

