5.5.2 Study Drug Preparation and Dispensing

Participants will receive one 40-count bottle of study drug at Visit 2, two 40-count bottles at Visit 3, and three 40-count bottles at Visits 4, 5, and 6. Study drug will be assigned in a double-blind manner via the IRT system at each applicable study visit.

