5.5.3 Study Drug Administration

All study drugs will be administered by the participant orally, once daily at approximately the same time on Days 1 to 365. Study drug should be administered with water.

At Visits 2, 5, and 7, participants should take study drug after a trough PK sample has been drawn.

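### The SAP's compliance rules count unreturned tablets as taken and drop long interruptions from the denominator, so the descriptive compliance summary is biased upwards

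*SAP*

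**What the plan says.** SAP 3.3.7 introduces one overall figure per participant: "The percentage overall compliance to study drug will be calculated using the following formula". The numerator is tablets dispensed minus tablets returned; there is no separate term for lost tablets. For missing drug the rule is: "If study drug is not returned, the number of tablets returned and lost will be considered 0 for the compliance calculation".

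Expected dosing days run from randomization to the earlier of end of treatment and early termination, less missed doses. Missed doses are defined as the "number of doses missed during IP interruptions due to AE or IP interruptions that are longer than 14 days". No restriction is placed on the reason for an interruption longer than 14 days.

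The result is "summarized by treatment group and in total based on the Safety Population and mITT On-Treatment", with categories <80%, 80% to 120% and >120%. The section ends: "Study drug interruptions due to AE or IP interruptions longer than 14 days will be listed".

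On supply, Protocol 5.5.2 gives each participant "one 40-count bottle of study drug at Visit 2, two 40-count bottles at Visit 3", and "three 40-count bottles at Visits 4, 5, and 6". Protocol 5.5.3 has study drug taken "once daily at approximately the same time on Days 1 to 365". Protocol 5.5.1 explains that the 40-tablet bottle includes an allowance for visit windows. Protocol 5.5.4 gives the same compliance formula, but neither defines expected dosing days nor says what to do about unreturned drug.

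**The concern.** Tablet count measures adherence only if a tablet that does not come back can be told apart from one that was swallowed. Here it cannot: a bottle left at home counts as fully taken, including the surplus supplied for visit windows. Separately, a long break in dosing leaves the denominator, so the doses missed in it no longer count against the participant. Protocol 4.3 lists failure to comply with the protocol among the reasons for a temporary discontinuation, so a long gap that is itself non-compliance can drop out of the compliance figure.

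At stake is how readers judge the dosing behind the safety results and the on-treatment analysis. The exposure summary in the same section does not correct the picture, because it is last dose date minus first dose date plus one and also ignores gaps. PK evidence is planned for the obicetrapib arm only, so for placebo the tablet count is the only planned quantitative measure of doses taken.

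**Working it through.** The documents state no compliance figure to reproduce, so this applies the SAP formula to the protocol's dispensing schedule.

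**Inputs**
- Dispensed (Protocol 5.5.2): 40 + 80 + 120 + 120 + 120 = 480 tablets.
- Planned doses (Protocol 5.5.3): one a day for 365 days.
- Compliance (SAP 3.3.7): 100 × (dispensed − returned) / expected dosing days.
- Visit days and windows (Protocol Appendix A): 30 ± 3; 84, 180, 270 and 365, each ± 7.

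**1. Nothing returned**
- At Day 365: 480/365 = 131.5%, whatever was taken.
- If treatment ends on the latest in-window day of a visit, before any new dispensing: 40/33 = 121.2%; 120/91 = 131.9%; 240/187 = 128.3%; 360/277 = 130.0%; 480/372 = 129.0%.
- All exceed 120%. Ending earlier within an interval raises the figure; a visit well beyond its window would lower it.

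**2. Some bottles not returned**

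The SAP does not say whether the zero rule works per bottle or per participant. That does not change these figures: the formula subtracts only what came back, so a kept bottle adds nothing to the returned count either way. Each full bottle kept adds 40/365 = 11.0 points, so one such bottle lets true adherence of 80 − 11.0 = 69.0% read as 80%.

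Assume uniform dosing, nominal visit days and all bottles dispensed as scheduled.

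| True adherence | Bottles kept | Returned | Reported |
|---|---|---|---|
| 60% | Visits 5 and 6 | 240 − 0.60 × 180 = 132 | (480 − 132)/365 = 95.3% |
| 50% | Visits 5 and 6 | 240 − 0.50 × 180 = 150 | (480 − 150)/365 = 90.4% |
| 70% | Visit 6 only | 360 − 0.70 × 270 = 171 | (480 − 171)/365 = 84.7% |
| 60% | Visit 6 only | 360 − 0.60 × 270 = 198 | (480 − 198)/365 = 77.3% |

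The first three move from <80% to 80% to 120%; the last does not. Closing each interval the day before the visit changes these by no more than 0.2 points (95.2% in the first row).

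**3. Gaps, with full dosing otherwise and all bottles returned**
- 14-day non-AE gap: the days stay in, 351/365 = 96.2%.
- 15-day gap: the days come out, 350/350 = 100%. Share of planned doses taken: 350/365 = 95.9%.
- 100-day gap: 265/265 = 100%. Share of planned doses taken: 265/365 = 72.6%. If dosing resumes and continues to Day 365, exposure also reads 365 days.
- The share of planned doses falls below 80% once the gap exceeds 0.20 × 365 = 73 days; the reported figure stays at 100%.

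**The case against.** A reader might infer that poor adherence is in general reported as full compliance. The documents do not support that. A participant who returns nothing, the plainest case under the rule, falls in >120% and so stands out, although the category cannot separate non-return from real over-use. Nor does the figure keep rising with the length of the gap: there is one step, between 14 and 15 days, and it applies to non-AE gaps only.

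A reader might also infer that the trial has no other adherence evidence, or that the efficacy result is at risk. Neither follows. SAP Table 1 adds a Day 84 PK assessment to check that drug is being taken, trough levels are an endpoint, and the mITT On-Treatment Population is defined by PK. Percent compliance enters no specified efficacy model, and the primary analysis is ITT under a treatment policy strategy. No compliance cut-off for the PP Population appears in either document.

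The gap rule can be defended as a definition: it describes adherence while dosing was meant to be under way, and removing AE interruptions fits that aim. The interruptions removed are listed, so they are not concealed. Protocol 5.5.4 asks sites to retrieve bottles and resolve tablet and day discrepancies in source, which should limit non-return. The documents give no non-return rate, and the 95.3% example needs a participant who keeps two successive dispensings yet is still counted to Day 365.

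All of this stands and limits the consequence. It leaves the direction of the bias unchanged. A listing does not put the lost days into the summary by arm, the source check does not override the SAP's zero rule, and PK says nothing about placebo.

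**Conclusion.** The point holds for the descriptive compliance summary. Both rules act upwards. Complete non-returners read above 120% (131.5% at Day 365). Under partial non-return, low takers can read as 80% to 120% (true 60% as 95.3% in the example). Any non-AE gap longer than 14 days stops counting, so a participant who took 72.6% of planned doses can read 100%.

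The non-return figures assume uniform dosing, nominal visits and full dispensing; how often this would occur cannot be judged from the documents. The gap figures assume full dosing outside one gap, and 72.6% is the share of planned doses, a different quantity from adherence while on drug. The primary ITT result is not affected. The change is worth making before database lock because the reported figure can mislead and the correction is cheap.

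**What to change.** In SAP 3.3.7:

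1. For any dispensing interval with unreturned bottles, set compliance for that interval to missing, dropping both its tablets and its days. Report the number of affected participants and intervals by arm, and state that the remaining figure describes those who returned their bottles. If non-returners adhere less well, that figure will still be somewhat high, which is why the counts are needed.
2. Keep the current while-on-drug version if wanted, labelled as such, and add a summary by arm that keeps all days from first dose to end of treatment in the denominator.

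The cost is SAP wording and a few lines of code. The downside is that compliance rests on fewer intervals for some participants, and the reported figures may be less favourable.
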